### **Analytical Plan**

See Outcomes Measures for the main plan of analysis.

Results will be analyzed initially using descriptive statistics. Comparison between groups will be done using chi square tests for proportions, and t-tests or ANOVA procedures for continuous variables. Regression analysis will be performed to identify independent outcome predictors. Other inferential statistical analysis will be conducted as appropriate.

### **Human Subjects Protection**

#### **Potential Risks**

The risks fall into three categories: risks associated with psychological assessment, risks associated with repetitive TMS and risks associated with MRI scanning.

#### **Risks of psychiatric interviewing (minimal risk):**

1. Some participants may get emotionally distraught when disclosing sensitive personal stories. Some participants may feel anxiety about disclosing substance use histories and reporting some aspects of their demographics.

#### **Risks associated with MRI scanning (minimal risk):**

1. The major potential risks for MRI are all subsumed under the risks for TMS and primarily include risks to individuals who have metallic implants, pacemakers, or pregnant women. These individuals will be excluded from the study.
2. Participants may feel restless or uncomfortable when lying in the MRI scanner.

#### **Risks associated with repetitive TMS (FDA-designated minimal risk):**

Repetitive TMS has been considered “non-significant risk” by the FDA (2007) when applied at similar intensities, durations, and frequencies to those being used in this protocol. Additionally medial prefrontal and dorsolateral prefrontal continuous theta burst stimulation in a manner identical to this protocol has been designated minimal risk by the MUSC Institutional Review Board for healthy adults as well as individuals with nicotine dependence.

1. **Potential risk of a seizure:** In designing this experiment, we have followed the latest safety guidelines for TMS. Despite these precautions, there is a chance of a seizure as a result of rTMS. Eight seizures have been noted in previous studies, with six of them occurring in healthy volunteers without any history of seizures, brain tumors or traumatic brain injuries. All of these seizures have occurred during rTMS with the participant in the treatment chair and a trained operator on hand. All seizures have stopped by themselves without any medication. No participants have had any problems after the seizures. WFUHS has a plan for dealing with fainting and seizures, and **every TMS researcher involved in providing TMS treatment for this protocol (Key Personnel) will have extensive TMS training from the PI on the study as well as a skills test associated with collecting an accurate motor threshold (which is one of the largest factors that promotes safety).** Additionally, if a participant has a seizure an emergency response team will be called. Most seizures, including those caused by rTMS, last less than 60 seconds and do not require any medication. Participants will be evaluated by a physician associated with the WFUHS Brain Stimulation Laboratory following recovery from the seizure. Any participant who has a seizure cannot continue with the study.

**A note about theta burst stimulation:** The relative risk of having a seizure is related to the strength of the TMS stimulation (% motor threshold) and the frequency (typically 1Hz-20Hz, or theta). There are

published safety tables for fixed frequency rTMS paradigms (eg 1hz, 5 Hz, 10 Hz, 20 Hz). For individuals receiving TMS doses within these ranges and without other risk factors, (medication, significant sleep deprivation, etc.), TMS has been deemed a non-significant risk by the FDA. For some brain stimulation protocols (like theta burst), there are no currently published safety tables, but there are at least 6 review articles that demonstrate that theta burst is likely minimal risk to non-significant risk. These studies largely show that the risks/safety of theta burst protocols are comparable (or perhaps less than) 10Hz or 20 Hz rTMS.

Other potential risks:

2. Potential for scalp discomfort and headaches: Some people report mild discomfort when the magnetic pulses are applied over the scalp. A small number of people (~5%) report headache following rTMS. However, the headaches are temporary and manageable with common over-the-counter pain remedies.
3. Potential hearing loss: The TMS coil generates a high-energy click that may cause hearing damage. Humans exposed to TMS have shown temporary increases in auditory threshold (especially at high frequencies) lasting at least 5 minutes and less than 4 hours.
4. Safety in case of pregnancy: This protocol will exclude pregnant women. The risks of using TMS with pregnant women are currently unknown. Please inform the research team if you are pregnant or think that you might have become pregnant during the study. A pregnancy test will be performed before the experiment begins.
5. Potential for reflex syncopal event: Syncope is defined as a momentary loss of awareness and postural tone. It typically has a rapid onset, short duration, and spontaneous recovery. Although syncopal episodes are very rare with TMS (less than 1%), they typically occur during the motor threshold procedure before the rTMS treatment has begun. Individuals that are sleep deprived and have low or unstable blood pressure are at greater risk.
6. Interaction with electrical or metal implants: Electrically, magnetically or mechanically activated implants (such as cardiac pacemakers), as well as clips on blood vessels in the brain may be affected by rTMS (as well as MRI) and cause pain or abnormal signal propagation. Therefore individuals that have these implants and devices or suspect that they may have pieces of metal in their eyes, head, or body (e.g. bullets, shrapnel, fragments from metallurgy) will be excluded from the study.

#### **Adequacy of protection against risks**

**(a) Recruitment and Informed Consent** Identification of Subjects, Recruitment of Subjects and Informed Consent Process. Advertisements will be placed in local print and digital media. Interested individuals will email, call, or text the research center and will then be contacted via telephone and scheduled for screening and Visit 1. Only individuals that have previously given permission to be contacted for future research purposes will be called. Informed consent will be reviewed with the potential participant by a member of the key personnel on this proposal. The consent will be signed by the participant as well as one of the Key Personnel on the proposal. A copy of the consent will be given to the subject and the original placed in the research record.

**(b) Security of Participant Information**

For individuals that are enrolled in the study (invited for a screening visit) there will be two documents that contain their first and last names: the informed consent that includes the written

HIPAA authorization and a receipt for their compensation kept for tax purposes. Each of these documents will be kept in a separate 3-ring binder.

Each individual enrolled in the study will be assigned a unique patient ID number (starting sequentially from '100'). A folder will be created for each of these participants and labeled with their Patient ID number. The folder will contain the results of all of the testing for each individual. The patients will only be identified by number, not by name, on these documents. All information stored digitally for the enrolled participants will be labeled with the Patient ID number. As above all of the participant folders, along with the binders will be stored in a locked cabinet in [name] research laboratory.

### **Protection Against Risks**

#### **Risks of psychiatric assessments:**

All psychiatric assessments will be conducted by study personnel who have received formal training in clinical interviewing and have worked with substance dependent patients in the past.

#### **Risks associated with MRI and TMS (minimal risk):**

1. Although the TMS protocol that we are using has never been associated with causing a seizure, individuals that have a history of seizures, stroke, or other neurological impairment that might lower their seizure threshold will be excluded from the study. All study personnel will have received a formal education course in seizure detection, care, and treatment and a physician will be available to immediately assist in stabilizing the participants in the event of a seizure. Any participant who has a seizure cannot continue with the study.
2. We will exclude individuals with claustrophobia such that they are not exposed to this risk. Additionally participants will be given a pressure sensitive squeeze ball that they can use to indicate at any time that they would like to leave the scanner.
3. To protect against hearing loss concerns, participants will wear high fidelity earplugs throughout the scanning session.
4. Participants will be informed of potential risk of scalp discomfort and headache before they consent and will be told that they should feel free to take non-steroidal antiinflammatory agents after the TMS session if they have a headache. We will also exclude individuals with chronic migraines such that they are not exposed to this risk.
5. We will exclude pregnant females such that they are not exposed to this risk.
6. All participants that enroll in this study will complete a written MRI safety screen. We will also use a handheld metal detector to ensure the participant has no metal in or on their body before entering the MRI scanning room.

**Protocol for participants expressing suicidal ideation:** All study team members performing the Becks Depression Inventory will have received online training from the Suicide Prevention Resource Center (<https://training.sprc.org>). Completion documentation will be saved on the laboratory drive. In the event that a participant expresses a desire to kill themselves (selects answer #2 or #3 on question #9 of the Becks Depression Inventory), the trained study team member will ask them about the level of detail of their thoughts. If the participant has a suicide plan to kill himself/herself, the study staff will recommend he/she speaks with the suicide hotline and initiate contact with the suicide prevention hotline (Durham Center Crisis Line at [name]) while the individual is in their presence. If the participant refuses to talk to the hotline and leaves, the study staff will call 911. The study staff member will also contact the PI via phone, email, or text as soon as possible to inform them of the situation.

Participants may withdraw from the study at any time or may be withdrawn from the study if the PIs feel it is in the best interest of the participant. All key personnel will undergo appropriate IRB training for dealing with human participants and will be trained by the PI at their site in all aspects of the study.

interventions. Personnel listed in this protocol (as well as any rotating medical students, graduate students, psychiatry residents or fellows that may be exposed to this investigation as part of their research training exposure) will be required to maintain their certification of HIPAA training and Protection of Human Participants in Research training on an annual basis. Any new personnel without experience in human clinical research will be encouraged to attend the WFU Core Clinical Research Training Course, which is offered live and online throughout the year. Through these measures we will ensure that all study staff will be trained and will maintain ongoing understanding of research ethics and the rights of the participant during the consenting process and throughout an individual's participation in the study.

In the event of a medical emergency, a research participant will be transported to the Emergency Department at WFUHS. If a psychiatric crisis occurs, the Department of Psychiatry at either hospital will be contacted to arrange for either an emergency outpatient appointment or an in house psychiatric consult.

### **Subject Recruitment Methods**

Participants with chronic pain will be recruited via flyers placed throughout the WFU campus, community, WFU clinics, broadcast messages, Craigslist, and via phone calls to individuals that have participated in previous studies with our group and have given permission to be contacted if other studies become available.

Advertisements will be placed around campus in approved locations, especially at WFU clinics. Other ads will be submitted to local newspapers as well as internet advertising to reach the general population (e.g. Craigslist, broadcast messages at WFU). Recruitment will also occur at community events where recruitment materials (such as pens, backpacks, and mugs) will be handed out to individuals. Interested individuals will call or text the research center and will then be contacted via telephone, phone screened, and scheduled for screening if eligible. If an individual declines study participation or is not eligible via phone screen, their information will be shredded and destroyed. Informed consent will be reviewed with the potential participant by a member of the key personnel on this visit. The consent will be signed by the participant as well as one of the Key Personnel on the proposal. A copy of the consent will be given to the subject and the original placed in the research record. The consent and HIPAA process will be done in [name] research laboratory and facility. The MRI scans will be done at the MRI center and the TMS sessions will be done in the TMS laboratory located in [name] research lab.

Additionally, a chart review will be conducted for research purposes. Potentially eligible patients will be identified. The potentially eligible patients in the PIs practice will be informed about the study as the PI feels is appropriate. Then potential patients who have agreed to be contacted for future research by logging their WFU Research Permissions preferences in MyChart will be contacted by phone and invited to participate. All other patients will be contacted through their providers to be informed of the study if the provider feels it is appropriate.

In 2016, the ratio of male:female individuals using opiates for pain was approximately 1:1. We will recruit in accordance with this ratio. There will be no exclusion criteria with respect to ethnic background.

### **Informed Consent**

Individuals that have previously consented to be contacted about future research studies will be contacted and phone screened to determine preliminary eligibility. They will be scheduled for their screening visit, which will take place in a private, quiet screening room in the Clinical Neuromodulation Laboratory space in [name] research suite. Informed consent will be reviewed with the potential participant by a member of the key personnel on this proposal. The consent will be signed by the participant as well as one of the Key Personnel on the proposal. A copy of the consent will be given to the subject and the original placed in the research record. All records will be stored in locked departmental files. Section

301(d) of the Public Health Service Act of November 4, 1988 also protects a layer of protection for the privacy of health information for individuals that engage in federally funded medical research.

### **Confidentiality and Privacy**

Confidentiality will be protected by collecting only information needed to assess study outcomes, minimizing to the fullest extent possible the collection of any information that could directly identify subjects, and maintaining all study information in a secure manner. To help ensure subject privacy and confidentiality, only a unique study identifier will appear on the data collection form. Any collected patient identifying information corresponding to the unique study identifier will be maintained on a linkage file, stored separately from the data. The linkage file will be kept secure, with access limited to designated study personnel. Following data collection subject identifying information will be destroyed three years after closure of the study, consistent with data validation and study design, producing an anonymous analytical data set. Data access will be limited to study staff. Data and records will be kept locked and secured, with any computer data password protected. No reference to any individual participant will appear in reports, presentations, or publications that may arise from the study.

### **Data and Safety Monitoring**

The principal investigator (PI) will be the primary party responsible for data management, oversight, and accountability in terms of participant safety and consent. A conflict of interest will be avoided by secondary evaluation of records by a Monitoring Entity (ME) (aka. data safety monitoring board- DSMB) on an annual basis. Quality control will include regular data verification (Integrity of the Consent and HIPAA, scores on assessments, MRI scanning information), study progress, subject status, adverse events, and protocol deviations. Protocol adherence will be monitored by the Wake Forest IRB, who will also be given access to the reports from the PI to the ME.

#### **Provisions to Monitor the Data to Ensure the Safety of Subjects**

**DSM Board Plan:** Meet annually with the PI to discuss the information listed in “Content of ME/DSM report”. This content of this meeting will be formalized in a report which will be circulated by email and digitally approved by the PI and ME/DSMB. The approved report will be sent to the Wake Forest IRB.

**Content of DSM Report:** The following information will be included in the DSM report- number of individuals consented, number of individuals enrolled, number of active participants, gender and race distribution of subjects, discussion and listing of all amendments to the proposal, any publications and/or scientific presentations related to the proposal, update on any resolved or unresolved AE/SAEs, review of any new scientific literature related to the safety and efficacy of this protocol.

**Plans for Interim Analysis of Efficacy Data:** Data from this study will be analyzed when a 50% recruitment goal is obtained. Final analysis will occur when all participants have finished the final follow-up phase of the study.

**Responsibility for Data and Safety Monitoring:** The PI, protocol-approved research team, and ME/DSMB are all responsible for data and safety monitoring. The PI will be most involved in data and safety oversight. The PI will discuss data integrity and inquire about safety/patient tolerance in weekly meetings with the research team.

**Data Entry Methods:** Data will be collected using REDCap™, which is a secure web application for building and managing online surveys and databases. REDcap™ supports online or offline data capture for research studies and operations. Participants and protocol-approved study personnel will enter data directly into the online portal to ensure security and prevent data loss.

**Data Analysis Plan:** Data for this study (behavioral assessments, functional MRI measurements) will be acquired by protocol-approved members of the research team, including graduate students and research specialists. These individuals will also perform data management and analysis under the guidance of the PI. Manuscript composition will be led by the PI and Co-Is, with the assistance of the research team.

**Quality Assurance Plan:** Weekly meetings will be held between the PIs and research team to discuss any data-related problems as well as qualitative comments received during data collection. Initial data analyses will examine distributions of variable scores, and comparability of baseline characteristics across conditions, any necessary adjustments to analyses will be made. Confidentiality protections are outlined below.

Statistical review of the study will be conducted annually by a Wake Forest biostatistician (including enrollment, retention, assessment inventories). Data collected in previous studies by our research group have demonstrated that after extended use in the MRI scanner environment (likely more than 5000 pulses) the strength of the induced magnetic field from the Magstim biphasic coil begins to drop in a non-linear fashion. Consequently, the intensity of the induced magnetic field from the Magstim coil will be assessed by protocol-approved study personnel and logged weekly (alongside with protocol use, number of pulses, intensity of pulses). This cumulative record of coil performance will be monitored and, when the intensity of the induced field had degraded 10%, we will switch to a new, identical Magstim coil.

**Definition and Reporting of AEs/SAEs to the IRB:** An adverse event (AE) is defined as any untoward medical occurrence in a study subject who was administered rTMS but does not necessarily have a causal relationship with this treatment. Any unwanted change, physically, psychologically or behaviorally, that occurs in a study participant during the course of the trial is an adverse event. A Serious Adverse Event (SAE) is defined as an adverse event that has one of the following outcomes: death, life-threatening, inpatient hospitalization or prolongation of existing hospitalization, persistent or significant disability/incapacity, a congenital anomaly/birth defect.

All unexpected AEs will be reported to the Wake Forest Institutional Review Board (IRB) and Committee on Human Research within 48-business hours. Serious AEs will also be reported within 24-business hours. Follow-up of all unexpected and serious AEs will also be reported to these agencies. AEs/SAEs are documented and reported as per IRB requirements. Research staff will identify AEs and obtain all available information to assess severity, seriousness, study relatedness, expectedness, outcome, and the need for change or discontinuation in the study intervention. AEs are documented on AE Logs and AE Case Report Forms. Additional relevant AE information, if available, will be documented in a progress note and stored in the research record as appropriate to allow monitoring and further evaluation. If the AE meets the definition for serious, appropriate SAE protocol specific reporting forms are completed and disseminated to the appropriate persons and within the designated timeframes as indicated above. For each AE/SAE recorded, the research staff will follow the AE/SAE until resolution, stabilization, or until the participant is no longer in the study as stated in the protocol. We will report adverse events to the Medical Wake Forest IRB online per the IRB's guidelines.

**Collection and Reporting of AEs and SAEs:** As mentioned above, all AEs/SAEs are documented and reported as per IRB requirements. Research staff will identify AEs, verify event with the participant, and obtain all available information to assess severity, seriousness, study relatedness, expectedness, outcome, and the need for change or discontinuation in the study intervention. AEs are documented on AE Logs and AE Case Report Forms. Additional relevant AE information, if available, will be documented in a progress note and stored in the research record as appropriate to allow monitoring and further evaluation. If the AE meets the definition for serious, appropriate SAE protocol specific reporting forms are completed and disseminated to the appropriate persons and within the designated timeframes as indicated above. If applicable, copies of medical records and injury reports will be retrieved and safely stored in the

subjects file. De-identified copies of reports will be sent to the Wake Forest IRB and ME/DSBM. For each AE/SAE recorded, the research staff will follow the AE/SAE until resolution, stabilization, or until the participant is no longer in the study as stated in the protocol.

**Reporting of Unanticipated Problems, Adverse Events or Deviations:** Any unanticipated problems, serious, and/or unexpected AEs, deviations or protocol changes will be reported within 24-72 business hours, depending on severity, by the principal investigator or designated member of the research team to the Wake Forest IRB and ME/DSMB.

**Management of SAEs or Other Study Risks:** As described above, SAEs will be immediately reported, within 24 business hours, to the ME/DSBM and Wake Forest IRB. For each SAE recorded, the research staff will follow the SAE until resolution, stabilization, or until the participant is no longer in the study as stated in the protocol. If applicable, copies of medical records and injury reports will be retrieved and safely stored in the subjects file. De-identified copies of reports will be sent to the Wake Forest IRB and ME/DSBM.

**Reporting of ME/DSMB Reports to IRB:** Any ME/DSMB reports will be reported to the Wake Forest IRB.

**Report of Changes or Amendments to the Protocol:** Any changes to the proposal/protocol must be approved by the Wake Forest IRB.

**Trial Stopping Rules:** The protocol will immediately be paused following notification of a SAE. Per IRB policy, the IRB and ME/DSMB will be notified within 24 business hours following the SAE notification. Should the reported SAE be confirmed as directly related to the protocol, the trial will be terminated. The device manufacturer will be notified within 72 business hours. Of note, according to the literature associated with the MagVenture device, there have been no clinical trials stopped or SAEs reported.

**Conflict of Interest:** Neither the PI, nor members of the research team have any Conflicts of Interest directly related to this protocol. The rTMS device used for the proposed study is manufactured by MagVenture.

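### Required follow-up of an adverse event, even a serious one, may end when the participant leaves the study while the event is still evolving

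*Combined protocol and SAP*

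**What the plan says.** The follow-up rule appears three times. Under Definition and Reporting of AEs/SAEs to the IRB, and again under Collection and Reporting of AEs and SAEs, staff are to "follow the AE/SAE until resolution, stabilization, or until the participant is no longer in the study as stated in the protocol". Under Management of SAEs or Other Study Risks, the rule for SAEs alone is to "follow the SAE until resolution, stabilization, or until the participant is no longer in the study as stated in the protocol".

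Other provisions describe how a participant's time in the study can end early:

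- Protection Against Risks: "Participants may withdraw from the study at any time or may be withdrawn from the study if the PIs feel" this serves the participant's interest.
- The same section, on MRI and TMS risks: "Any participant who has a seizure cannot continue with the study".
- Trial Stopping Rules: "Should the reported SAE be confirmed as directly related to the protocol, the trial will be terminated".

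Several duties run alongside the follow-up rule. The IRB reporting section says "Follow-up of all unexpected and serious AEs will also be reported to these agencies", and asks staff to collect what information can be had on each event, its outcome included. Medical records and injury reports are retrieved where relevant. The annual report to the monitoring board covers both resolved and unresolved events. After a seizure, "Participants will be evaluated by a physician associated with the WFUHS Brain Stimulation Laboratory following recovery from the seizure".

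**The concern.** The usual expectation is that an SAE is followed until its outcome is known or the participant's condition is stable, whether or not the person still attends study visits. Here exit is a third, free-standing end point, and it applies to SAEs on the same terms as to any minor event. An adverse event is also an obvious reason for withdrawing, or for being withdrawn, so the event that most needs following may itself cause the exit that ends the duty.

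At stake are the protection of a participant with an open serious event and the completeness of SAE outcomes. The latter has some added value here: the protocol says that no safety tables have been published for theta burst stimulation, and that the literature associated with the device reports no SAEs.

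**Working it through.** No arithmetic applies. The check is to set the provisions side by side.

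**1. Structure of the clause.** Follow-up runs until (a) resolution, (b) stabilisation, or (c) the participant has left the study. Because these are joined by *or*, (c) is sufficient alone. An event that meets neither (a) nor (b) need not be followed further once (c) is met.

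**2. SAEs against other events.** The SAE-only statement lists the same three end points as the general one. SAEs are reported faster, but they are not required to be followed longer.

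**3. What counts as having left.** The clause ends by pointing back to the protocol, but no visible section defines the term. It could mean any exit, or only the end of protocol-defined participation. Under either meaning, an event still evolving at that point falls outside the stated duty.

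**4. Routes to exit.** These are withdrawal by the participant, withdrawal by the investigators, termination of the trial after a related SAE, and the end of scheduled follow-up. Early exit is expected: the Sample Size section allows for up to 20% dropout by the end of Week 4. No visible section says that open events continue to be followed after any of these.

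**5. Which events are left exposed.**

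- *Seizure.* It does end participation, but the protocol says most last under 60 seconds and provides a physician evaluation afterwards. A typical seizure would meet (a).
- *Lasting disability.* The SAE definition includes "persistent or significant disability/incapacity". Once such a condition is stable, it meets (b).
- *Event still changing at exit.* It meets neither (a) nor (b), and only (c) applies. This is the gap.

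**6. Other duties against the end point.**

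| Duty | What it adds | Does it remove end point (c)? |
|---|---|---|
| Collect available information, including outcome | An unconditional collection duty with no exit cut-off in its own sentence | No; it sets no duration and leaves the follow-up clause as it is |
| Report follow-up to the IRB | Makes whatever follow-up is done visible | No; it gives no period |
| Retrieve records | May reveal the outcome | No; it applies only where relevant |
| Annual monitoring report | Keeps open events in view | No; it reports status |

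Together these make loss of an outcome less likely. They do not change the rule that staff are told to apply.

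**The case against.** The strongest reply is that the rule does not stand alone. The duty to collect outcome information is a real collection duty, not merely a reporting one, and nothing in its sentence stops it at exit. An SAE also pauses the protocol at once, and the IRB and monitoring board are told within 24 business hours, so two oversight bodies know of the event before any termination. The words pointing back to the protocol can reasonably be read as protocol-defined participation, and no section says that termination makes the affected person a non-participant for safety purposes. Consent pages and IRB requirements were not available for this review and may add duties.

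Most of this stands, and it makes the point smaller. It does not answer it, because the same explicit end point appears three times, once for SAEs alone, and duties held elsewhere would not correct that text.

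A reader might infer three stronger things that the documents do not support:

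- *That seizures or permanent disabilities would go unfollowed.* Typical cases meet resolution or stabilisation.
- *That SAE outcomes would be lost.* They might still be learned through the other duties; loss is possible, not certain.
- *That the shortfall can be measured in weeks by subtracting the week of onset from the last week in Table 1.* Measured against stopping at once, that needs an assumed exit in the week of onset. It ignores timing within the week, and it treats the last column as everyone's exit date, which the text does not say. It also says nothing about harm.

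**Conclusion.** The point holds in a limited form. As written, required follow-up of an adverse event or SAE may end at study exit although the event is neither resolved nor stable, and SAEs have no longer window than other events. The exposure is limited to events still evolving at exit. The other safety duties partly mitigate it without removing it.

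Its size cannot be put as a number, because the documents give no rate of events open at exit. It is a matter of participant protection and complete SAE outcomes; no treatment estimate, power figure or error rate changes. The conclusion rests on the visible text and on reading the three end points as alternatives. It does not claim that staff would in fact stop, or that the consent form and IRB rules are silent. It is a cheap improvement worth making, not a serious flaw in the trial.

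**What to change.** In all three places where the rule appears, add a sentence to this effect: SAEs, and adverse events that lead to withdrawal, will be followed to resolution or stabilisation whether or not the participant is still in the study or the trial has been terminated, unless the participant declines further contact. Other adverse events can keep the present rule.

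The means are already in place. Exclusion criterion 10 rules out anyone without a stable phone number, and under Confidentiality and Privacy identifying information is kept until three years after study closure.

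The cost is matching wording in the consent form and a few calls per open event, with no new staff or procedure. The downside is that some calls may fall after the last scheduled visit, or after the planned completion at 22 months. The gain is partial for participants who withdraw and decline contact.
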